9.1 Institutional Review Board (IRB) Review

The protocol will be submitted to the IRB for review and approval. Approval of the protocol must be obtained before initiating any research activity. Any change to the protocol will require an approved IRB amendment before implementation. The IRB will have final determination whether informed consent and HIPAA authorization are required.

Study closure will be submitted to the IRB after all research activities have been completed.

Other study events (e.g. data breaches, protocol deviations) will be submitted per Yale policies.

9.2 Research Personnel Training

All individuals assisting with conduct of research will receive and/or have received human subjects research training. Community members have completed CITI human subjects research training. Research assistants will be involved in curriculum administration and data collection over Zoom, with training and oversight by the PI.

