1.2 Prior Experience

In response to stakeholder-identified concerns related to delayed identification of MBH problems and lack of coordinated referrals, we partnered with community members to conduct interviews with Afghan refugee parents. From this community-based participatory research (Rosenberg, J., Leung, J. K., Harris, K., Abdullah, A., Rohbar, A., Brown, C., & Rosenthal, M. S. (2021). Recently-arrived Afghan refugee parents' perspectives about parenting, education and pediatric medical and mental health care services. *Journal of Immigrant and Minority Health*), we learned that many parents had not yet considered or reflected on MBH concerns because of higher priority concerns around safety and acculturation. Parents described priorities around health that were related to basic safety after living in war-torn regions. They described an emerging support system and an appreciation for an engaged and connected health system but expressed little trust in discussing MBH concerns with medical providers. Based on parents' identified needs and opportunities for engagement, we sought opportunities for education, prevention, and engagement with community members.

In summer 2020, we developed and launched an adaptation of an SEL curriculum, "EMPOWER," with 13 families to establish community trust, determine program feasibility,

and to promote public health by disseminating preventative COVID-19 information in preferred languages. We analyzed the program after its conclusion by surveying and interviewing parents of each participating family. Findings from this analysis, which were recently published in *Health Education Behavior* (Rosenberg, J., McDonough Ryan, P., O'Brien, C., Ganjavi, F., & Sharifi, M. (2021). Pilot Wellness Program With Adapted Social-Emotional Learning and COVID-19 Curriculum for Refugee Youth. *Health Education & Behavior*), suggest that the curricular components are likely to be feasible and acceptable. After the program, all 13 parents who participated correctly identified symptoms and protective measures for COVID-19 based on a published questionnaire that assessed disparities in COVID-19 knowledge.¹⁷ Additionally, all parents responded that the program was worthwhile, that they were interested in re-enrollment, and that they would recommend EMPOWER to a peer. However, social desirability bias, a small sample, and the lack of a comparisons group limit our interpretation of these preliminary results.

2 Rationale/Significance

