5.1 Study Population

Participants will include families who are connected with Elena's Light, a trusted community non-profit organization that supports refugee families in the New Haven region.

Waitlist control participants will receive written, translated program materials and begin the formal curriculum after the intervention group.

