6.1 Study Procedures

EMPOWER Curriculum: EMPOWER is an adapted SEL and wellness education initiative delivered to a community of refugee families that was developed through a pre-pilot in the New Haven Afghan refugee community in 2020. Unlike traditional school-based SEL curricula, EMPOWER partners with community organizations to provide translated and trauma-informed wellness education to family units. The program combines in-person (socially distant) and remote delivery of culturally-informed physical, emotional, and medical wellness tools adapted from evidenced-based behavioral medicine, refugee trauma and recovery, and community health research (Table 2). Over two weeks, enrollees participate in six in-person sessions (two hours each). They also complete four, one-hour, weekly Zoom sessions during and beyond the in-person curriculum. At-home Zoom technical support is provided as needed. Each family unit is guided through in-person and online components by a facilitator. The EMPOWER curriculum focuses on the core competency of self-awareness, a core element of emotional competence, from the Collaboration for Academic Social and Emotional Learning (CASEL) framework.²³ Facilitators include interns, health-providers, and community partners. We have published a detailed EMPOWER manual, which we will iteratively modify, through an online request portal.²⁴

Intervention: We will use implementation science methods and apply an Intervention Mapping framework to refine and assess the adoption, acceptability, and feasibility of EMPOWER.¹⁸ The program will include virtual and in-person SEL, COVID-19 safety, and physical activity instructions. Program administrators will also respond to and track disclosure of and/or identification of mental health, medical, or other needs.

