Data Collection and Measures: We will conduct a mixed methods evaluation—using concurrent qualitative and quantitative data collection and merged analysis²⁵—to survey parents and their children (over Zoom) at early and late time-points of their involvement in the program. Interview guides and survey tools will be developed with community partners and will be based upon previously-studied measures used for war-affected families.²⁶ In addition to demographic covariates (age, gender, languages, years in the US), we will collect data and assess implementation outcomes as well as primary and secondary outcome measures (Table 1). Questions will be asked to parents about each child and to the children directly.

Implementation measures (Aim 1) will include assessment of adoption, acceptability, and feasibility through parent and stakeholder evaluations and through rates of attrition. Outcome measures (Aim 2) will include (a) COVID-19 knowledge, measured via an established COVID-19 knowledge assessment¹⁷ and (b) children's SEL competence, measured by the Trait Meta-Mood Scale.¹⁶ Secondary outcomes and covariates will include the validated measures outlined in Table 1 that may modify intervention effectiveness. While timeline and small sample size in this pilot will likely not allow detection of pre-post differences in quality of life or behavioral health concerns such as stress or depressive symptoms, we will examine patterns in secondary outcomes to form hypotheses in preparation for future, larger-scale trials.

Table 2. EMPOWER Curricular Components

Pre-EMPOWER Preparedness

At Home: Consent Form Signed, Materials Delivered
At Home: Zoom Support, Zoom Orientation with Parents
Identification of Outdoor Space, Safe and Walkable

In-Person Curriculum (6 times, over 2 weeks)

COVID-19 symptom and temperature check
Hand-washing, clean space, social distance
Arrival art activity and materials provided
Lesson: COVID-19 Safety (symptoms and prevention)
Lesson: Physical Activity (eg breathing, yoga)
Lesson: Healthy Habits (eg healthy eating)
Lesson: SEL, Emotional Vocabulary (eg emotion bingo)
Lesson: Art Activity (eg painting emotions)
Wrap-Up: Homework, Breathing, Hand-Washing

Zoom Curriculum (1 time weekly, over 4 weeks)

Arrival: Mindfulness Exercises (eg 20 Questions)
Lesson: COVID-19 Safety (symptoms and prevention)
Breakout Lesson: Physical Activity (eg yoga)
Breakout Lesson: Homework check-in
Breakout Lesson: SEL, Emotional Vocabulary Games

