Wrap-Up: Homework, Next Meeting

Intervention and Evaluation Schedule

	Info Session (All)	Pre- Evaluation (All)	EMPOWER (for Intervention Group)	Evaluation (Intervention)	Evaluation (Control)	EMPOWER (for Control Group)
Zoom Information Session	X					
Zoom Informed Consent		X				
Demographic Collected		X				
Outcome Evaluation						
COVID-19 Knowledge		X		X	X	
Trait Meta Mood Scale		X		X	X	
Secondary Outcomes: Afghan Symptom Checklist, PedsQL, PSC		X		X	X	
Implementation Outcomes				X		
EMPOWER Curriculum			X			X

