6.1.1 Data Collection

After confirming verbal informed consent, data will be collected over Zoom with interpreters who speak the respondents' preferred languages.

- **Translated Data Collection Instruments**: Standardized data collection tools, which will be interpreted according to World Health Organization Standards include:
 - Trait meta mood scale¹⁶
 - Afghan symptom checklist²⁰
 - Pediatric quality of life²⁷
 - Perceived stress scale¹⁹
 - COVID-19 questionnaire,¹⁷ previously administered (uploaded in supporting documents)
- **Implementation Outcomes**: A qualitative survey guide will be developed with stakeholders to discuss feasibility and acceptability with parents, based upon prior piloted survey tools (uploaded in supporting documents).
- **Mode of Data Collection**: All surveys and interviews will be conducted over Zoom. After verbal informed consent is read in the respondent's preferred language, with permission, responses will be audio-recorded. Interviews will be transcribed verbatim in real-time with post-interview proofreading and comparison to the audio recordings. It is expected that all interviews and surveys will be approximately one hour in duration.
- **Compensation**: A \$25 gift card will be distributed to respondents after each interview. All interviews were approximately one hour in duration.

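### Nothing in the protocol stops research assistants from interviewing families they taught, and at the second evaluation only intervention families could be affected

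*Combined protocol and SAP*

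**What the plan says.** Section 9.2 is the only place that describes what research assistants do in the study beyond consent and training: "Research assistants will be involved in curriculum administration and data collection over Zoom", with training and oversight by the principal investigator. Section 6.1 adds that "Each family unit is guided through in-person and online components by a facilitator" and lists facilitators as interns, health providers and community partners, without naming research assistants.

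Section 6.1.1 states that "All surveys and interviews will be conducted over Zoom", with interpreters. Section 6.1 states that "Questions will be asked to parents about each child and to the children directly". Table 1 names parents and children as respondents for the Trait Meta-Mood Scale, COVID-19 knowledge and all secondary scales.

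Under section 5.1 the wait-list controls "begin the formal curriculum after the intervention group". The schedule in section 6.1 places the control group's second evaluation before its curriculum. The same schedule marks implementation outcomes only at the intervention group's evaluation. Section 7.2 makes the primary analysis a comparison of pre-post change between the two groups, using a repeated measures linear mixed model.

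In section 1.2 the team says of its 2020 pre-pilot that "social desirability bias, a small sample, and the lack of a comparisons group limit our interpretation of these preliminary results".

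**The concern.** The outcomes are mostly self-report or parent-report, given aloud to a member of the study team. A family answering someone who has just taught its children may give kinder answers than it would give to a stranger. If this happened equally in both groups, it would cancel in the comparison of change. Here it cannot be equal: at the second evaluation no control family has yet been taught, so only intervention families can be facing their own teacher.

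Any such shift enters the primary contrast directly and looks like a programme effect. The mixed model cannot separate the two, because the shift coincides with group and time. The comparison group answers one of the pre-pilot limits that the team listed, but it does not answer social desirability that differs between groups.

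**Working it through.** **Who measures whom.** Set side by side, the sections give the following.

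- Section 9.2 gives assistants both duties. No section provides independent or blinded assessors, or a rule against evaluating one's own families.
- At the first evaluation nobody in this study has been taught. At the second, intervention families have been taught and controls have not (section 5.1; schedule in section 6.1). The possible teacher effect is therefore confined to one cell of the group-by-time layout, the cell that identifies the treatment effect.
- The safeguards stated are observed data collection sessions in training (8.2), oversight by the principal investigator (9.2) and a mentor outside administration and evaluation (9.3). None separates teaching from interviewing.

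**Which outcomes.** The Trait Meta-Mood Scale and the stress, quality-of-life and symptom measures are reports by parents and children, so they are exposed. COVID-19 knowledge is closer to a test. Courtesy matters less there, and prompting or lenient scoring would be the likelier route. Acceptability and feasibility are assessed only in the intervention group, so courtesy there inflates a one-arm result and is a separate problem from the group comparison.

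**Scale, for illustration.** Section 7.1 gives no alpha, power, SD or numeric effect size, so there is no figure of the plan's to reproduce.

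Inputs from the documents: 50 children in 20 families against 25 children in 10 families (7.1), which is 50/20 = 25/10 = 2.5 children per family.

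Assumptions: SD of change = 1, two-sided alpha 0.05, no true effect, and an average shift b over all 50 intervention children. With family correlation (ICC), the standard error is taken to allow for it correctly.

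- Design effect DE = 1 + (2.5 − 1) × ICC. For ICC 0.3, DE = 1.45.
- SE = √[DE × (1/50 + 1/25)] = √(0.06 × DE). This is 0.245 for ICC 0 and √0.087 = 0.295 for ICC 0.3.
- False-positive rate = Φ(b/SE − 1.96) + Φ(−b/SE − 1.96).

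| Average shift b | b/SE, ICC 0 | Rate, ICC 0 | b/SE, ICC 0.3 | Rate, ICC 0.3 |
|---|---|---|---|---|
| 0 | 0 | 5.0% | 0 | 5.0% |
| 0.1 SD | 0.41 | 6.9% | 0.34 | 6.3% |
| 0.2 SD | 0.82 | 12.9% | 0.68 | 10.4% |
| 0.3 SD | 1.22 | 23.2% | 1.02 | 17.4% |

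With ICC 0.4 the rates are 6.2%, 9.9% and 16.2%. The rate falls with ICC only because the SE grows; the bias in the estimate is b throughout.

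**Partial overlap.** If a fraction f of intervention children are evaluated by someone who taught them and each such child shifts by d, then b = f × d. With f = 0.5 and d = 0.2 SD, b = 0.1 SD, and the rate at ICC 0 is about 7% instead of 13%.

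**The case against.** The strongest reply is that permitted overlap is not actual overlap. A reader might infer from section 9.2 that assistants will interview the families they taught, or that the results will be biased. The documents support neither. They do not say which assistant evaluates which family, they leave curriculum administration undefined, and the list of facilitators does not name research assistants. That reply stands: what is established is the absence of a rule, and the amount of bias is unknown.

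Second, this is a pilot for preliminary efficacy with no stated alpha, so false-positive rates are not its currency. That is fair. The direct measure is the shift itself, and the rates only show how it compares with the standard error at this sample size.

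Third, the control group cancels courtesy common to both groups. That is true, since controls also meet the team, receive written materials and await the programme. Only the excess in the intervention group matters, and the teacher-specific part of it does not cancel.

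Fourth, a reader might take the illustrative rates as what a new rota would save. They are not. Intervention families know that they took EMPOWER and would still be answering its study team, through interpreters, after recruitment by the partner organisation. Courtesy toward the programme would survive a change of interviewer.

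Finally, the number of assistants and their allocation to groups are not stated, so it cannot be asserted that separation is always possible with current staff.

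**Conclusion.** The point holds as a gap in the design. Teaching and outcome interviewing are given to the same staff category, nothing keeps an assistant from evaluating a family he or she taught, and the timing of the control evaluation means that any resulting courtesy falls on one group only. Its direction would favour EMPOWER on the Trait Meta-Mood Scale, one of the two primary efficacy measures, and on the secondary scales. COVID-19 knowledge is less exposed. Acceptability is affected as a one-arm result.

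The size cannot be derived from the documents. Under the stated assumptions, an average shift of 0.1 to 0.3 SD would take a nominal 5% false-positive rate to about 7% to 23%, or 6% to 17% with an assumed ICC of 0.3. Less than full overlap reduces the average shift proportionately. Confidence is high that the separation is missing from the text and limited as to how much bias would follow. The gap is worth closing before data collection, because it cannot be repaired afterwards.

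**What to change.** Add to sections 9.2 and 6.1.1, in words such as these: *Using existing staff, the second evaluation and the acceptability interview of each family will be conducted by an assistant, and where possible with an interpreter, who did not teach or facilitate that family. Interviewers for both groups will be drawn from the same rota. Interviewer identity will be recorded at each evaluation. Where staffing makes separation impossible, the overlap will be reported and a sensitivity analysis will exclude those interviews.*

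This looks workable. Section 7.1 caps in-person attendance at ten children, which for 50 children implies about 50/10 = 5 teaching groups, and section 9.2 speaks of assistants in the plural, so interviewers could be swapped between groups. If assistants rotate through all groups, the fallback of recording, reporting and sensitivity analysis applies.

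The cost is a short protocol addition, one more recorded item, some scheduling effort and some lost rapport in the interviews. The curriculum, sample and instruments are unchanged. The report should still list courtesy toward the programme itself as a limitation, because the rota does not remove it.

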9.3 Study Monitoring

The internal team will monitor the study. A research mentor will not be involved directly in study administration or evaluation but will provide oversight of accuracy and rigor of evaluation. The research mentor, [name] MD MPH, will meet with the PI weekly and will review and contribute to all research products.

9.4 Unanticipated Problems and Protocol Deviations

A protocol deviation is any noncompliance with the protocol. The noncompliance may be either on the part of the participant, the investigator, or the study site staff. As a result of deviations, corrective actions are to be developed by the site and implemented promptly.

It is the responsibility of the site investigator to identify and report deviations within 10 working days of identification of the protocol deviation. All deviations must be addressed in study source documents, reported to the study sponsor, and the reviewing Institutional Review Board (IRB) per their policies.

Unanticipated problems involving risks to participants or others include, in general, any incident, experience, or outcome that meets all of the following criteria:

- Unexpected in terms of nature, severity, or frequency given (a) the research procedures that are described in the protocol-related documents, such as the Institutional Review Board (IRB)-approved research protocol and informed consent document; and (b) the characteristics of the participant population being studied;
- Related or possibly related to participation in the research ("possibly related" means there is a reasonable possibility that the incident, experience, or outcome may have been caused by the procedures involved in the research); and
- Suggests that the research places participants or others at a greater risk of harm (including physical, psychological, economic, or social harm) than was previously known or recognized.

If the study team becomes aware of an unanticipated problem (e.g. data breach, protocol deviation), the event will be reported to the IRB by the PI contacting the IRB.

The UP report will include the following information:

Protocol identifying information: protocol title and number, PI's name, and the IRB project number;

- A detailed description of the event, incident, experience, or outcome;
- An explanation of the basis for determining that the event, incident, experience, or outcome represents an UP;
- A description of any changes to the protocol or other corrective actions that have been taken or are proposed in response to the UP.

To satisfy the requirement for prompt reporting, UPs will be reported using the following timeline:

- UPs will be reported to the IRB within ten days of the investigator becoming aware of the event.

9.5 Study Discontinuation

The study would be discontinued if there were any concerns related to safety or efficacy by any members of the research team and/or the IRB and/or the study sponsor.

9.6 Study Completion

Data analysis is expected to be complete around March 2023, and IRB will be notified upon completion.

9.7 Conflict of Interest Management Plan

The independence of this study from any actual or perceived influence, such as by the pharmaceutical industry, is critical. Therefore, any actual conflict of interest of persons who have a role in the design, conduct, analysis, publication, or any aspect of this trial will be disclosed and managed. Furthermore, persons who have a perceived conflict of interest will be required to have such conflicts managed in a way that is appropriate to their participation in the trial. The study leadership in conjunction with the appropriate conflict of interest review committee has established policies and procedures for all study group members to disclose all conflicts of interest and will establish a mechanism for the management of all reported dualities of interest.

All investigators will follow the applicable conflict of interest policies.

9.8 Funding Source

This work is funded in part by the Academic Pediatrics Association, Yale University Department of Pediatrics and NIH/NCATS.

9.9 Publication Plan

It is expected that the PI, [name], will hold the primary responsibility for publishing the study results, with guidance from the funding agencies (listed above) and from her mentor in the Department of Pediatrics, [name].

The PI of this proposal are committed to the open and timely dissemination of research outcomes. The data generated in this grant will be presented at national or international conferences and published in a timely fashion. All final peer-reviewed manuscripts that arise from this proposal will be submitted to the digital archive PubMed Central.

The principal investigator will ensure that clinical trial(s) under the award are registered and results information is submitted to ClinicalTrials.gov as outlined in the policy and according to the specific timelines stated in the policy. The recipient institution has an internal policy in place to ensure that clinical trials registration and results reporting occur in compliance with policy requirements. The principal investigator will also be responsible for aggregate results reporting and AE reporting at the conclusion of the project.

10 List of Tables

Table 1. EMPOWER Outcome Measures, Instruments, and Respondents		
Implementation Outcome Measures (via Qualitative Evaluations):		
Feasibility	Qualitative evaluation of parents' challenges with feasibility. Community partner stakeholders will be involved in this analysis.	Parents
Attrition	Participant attendance & reasons for absence	Parents
Parent and Child Acceptability	Qualitative evaluation of (1) parents' experiences (2) child completion of homework activities (3) referrals (for parents and children) related to mental, emotional, physical or behavioral health	Parents
Primary Outcome Measures (via Pre- and Post-Tests):		
COVID-19 Knowledge	Evaluation of Symptoms and prevention* ¹⁷	Parents & Children
Social-Emotional Competence	Trait Meta-Mood Scale* ¹⁶	Parents & Children
Secondary Outcomes Measures and Covariates (via Pre- and Post-Tests):		
Quality of Life	Pediatric Quality of Life Inventory (PEDS-QL)*	Parents & Children
Stress	Perceived Stress Scale (PSC)* ¹⁹	Parents & Children
Depressive Symptoms	Afghan Symptom Checklist (CBCL) ^{‡20}	Parents & Children
Social Problems	Afghan Symptom Checklist (CBCL) ^{‡20}	Parents & Children
*To be translated according to World Health Organization Standards. ²² ‡Pashto/Farsi translation available.		

Table 2. EMPOWER Curricular Components	
Pre-EMPOWER Preparedness	
At Home: Consent Form Signed, Materials Delivered	
At Home: Zoom Support, Zoom Orientation with Parents	
Identification of Outdoor Space, Safe and Walkable	
In-Person Curriculum (6 times, over 2 weeks)	
COVID-19 symptom and temperature check	
Hand-washing, clean space, social distance	
Arrival art activity and materials provided	
Lesson: COVID-19 Safety (symptoms and prevention)	
Lesson: Physical Activity (eg breathing, yoga)	
Lesson: Healthy Habits (eg healthy eating)	
Lesson: SEL, Emotional Vocabulary (eg emotion bingo)	

Lesson: Art Activity (eg painting emotions)
Wrap-Up: Homework, Breathing, Hand-Washing
Zoom Curriculum (1 time weekly, over 4 weeks)
Arrival: Mindfulness Exercises (eg 20 Questions)
Lesson: COVID-19 Safety (symptoms and prevention)
Breakout Lesson: Physical Activity (eg yoga)
Breakout Lesson: Homework check-in
Breakout Lesson: SEL, Emotional Vocabulary Games
Wrap-Up: Homework, Next Meeting
